**NCT03175679**

**March 1, 2017**

## **Background**

Invariant Natural Killer T (iNKT) cells activated by a specific glycolipid antigen (a-galactosylceramide) show strong antitumor activity against malignant tumor through producing high levels of cytokines, such as IFN- $\gamma$  and IL-4. iNKT cells and their frequencies are abundant in the liver, but defect in malignant tumor development. We did a phase I dose escalation study with autologous in vitro expanded iNKT cells in advanced hepatocellular carcinoma (HCC).

## **Objectives**

Inclusion criteria included diagnosed of HCC by CT or MRI, BCLC B/C stage, age 18 to 80 and predicted life span of 12 weeks or more to complete the study and follow-up. Exclusion criteria included uncontrolled systemic diseases, central nervous system metastases or other tumor, unstable immune system disease, positive HIV, syphilis or immune deficiency disease and known hypersensitivity immunotherapy and related drugs. All patient understood and voluntarily signed the informed consent.

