## **Method**

Patients underwent leukapheresis to collect circulating iNKT cells, which were isolated using a monoclonal antibody (6B11) against the invariant TCR- $\alpha$  chain expressed by iNKT cells and expanded in culture over 14 days. The expanded cells were harvested and divided into 3 doses. The expansion rates of iNKT cells in enrolled patients before and after

cultivation were analysed by flow cytometry analysis. Realtime-PCR was conducted to compare the mRNA level of Th1 and Th2 cytokines before and after iNKT cultivation.

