### **Stuty design**

Patients were intravenously doped with different doses of autologous iNKT cells, 3 infusions per course. Dosages were escalated from  $3 \times 10^7$  cells/m^2 to at least  $9 \times 10^7$  cells/m^2. Tegafur will be given twice per day for 2 weeks after apheresis. Human IL-2 will be given during 5-14 days after iNKT cells infusion. Subjects were monitored for 4 weeks post-infusion to make sure the safety of this therapy. The laboratory safety tests and physical examination were carried out at 2nd week, 4th week, 8th week and 12th week after iNKT infusion. All subjects were followed every 3 months until the disease progressed.

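### Does the 12-week life-span criterion fall short of the last scheduled safety visit?

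*Combined protocol and SAP*

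**What the plan says.** The eligibility text, placed under Objectives, asks for a "predicted life span of 12 weeks or more to complete the study and follow-up". It names no starting date for the prediction and no method of making it.

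Under Method, leukapheresis comes first. The cells are then "expanded in culture over 14 days", harvested, and split into three portions for infusion.

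The Study design section (spelled Stuty design in the document) specifies "3 infusions per course" without giving the spacing. Safety checks are set at weeks 2 and 4, then at the "8th week and 12th week after iNKT infusion"; which of the three infusions starts that clock is not stated. On shorter-term safety it says: "Subjects were monitored for 4 weeks post-infusion to make sure the safety of this therapy". On longer follow-up: "All subjects were followed every 3 months until the disease progressed".

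The Statistical Analysis Plan covers two outcomes only, cell expansion and cytokine mRNA, each compared before and after culture.

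**The concern.** The criterion comes with a reason: the patient should live long enough to finish. That invites a check against the visit schedule. An inclusion criterion is normally judged before the first study procedure, which here is leukapheresis. Infusion cannot come before the end of culture, so the 12-week visit is more than 12 weeks away when the patient is assessed. A patient predicted to live between 12 and 14 weeks would satisfy the number yet not be predicted to reach the last safety visit.

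Late safety data would be at stake. In a phase I dose-escalation study in advanced hepatocellular carcinoma, the follow-up visits carry much of the information. If patients near the limit die or decline before week 12, their last visit could simply be blank, and the SAP has no rule for counting them.

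**Working it through.** **Inputs**
- Life-span criterion: 12 weeks (Objectives).
- Culture time: 14 days, so 14 / 7 = 2 weeks (Method).
- Safety visits: 2, 4, 8 and 12 weeks after infusion (Study design).
- Safety monitoring: 4 weeks after infusion (Study design).
- Infusions: 3 per course, spacing not given (Study design).

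The plan does not derive its 12 weeks from the schedule, so there is no calculation of its own to reproduce. The check is whether the two fit.

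**Origin at leukapheresis, visits from first infusion, infusion on the day of harvest**

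Visit time = culture time + weeks after infusion:
- 2 + 2 = 4
- 2 + 4 = 6
- 2 + 8 = 10
- 2 + 12 = 14

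Three visits fall within 12 weeks. The fourth exceeds it by 14 − 12 = 2 weeks. The 4-week monitoring ends at 2 + 4 = 6 weeks, well inside.

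**Origin at first infusion for both life span and visits**

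The last visit is at week 12, and 12 − 12 = 0. The criterion just covers it.

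**Origin at leukapheresis, visits from last infusion**

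Let the three infusions span d weeks. The last visit is at 14 + d. Assuming d = 1, 2, 3 or 4 gives weeks 15, 16, 17 or 18. The week-8 visit falls at 10 + d, which passes 12 only when d exceeds 2. The 4-week monitoring would end at 6 + d, at most week 10 over this range. These values of d are assumptions; they show only that the spacing is unstated.

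**Open-ended follow-up**

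Three-monthly follow-up runs to progression and has no fixed end. Its first visit, about 13 weeks after infusion (365.25 / 4 / 7 = 13.04), already lies beyond 12 weeks on any of these origins. No finite life-span figure could guarantee this part of the follow-up.

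**Effect on the analyses**

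Both SAP outcomes compare cells before and after culture, so their data come from the 2-week culture period. Reaching or missing a visit at week 14 does not enter either comparison.

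**The case for a change.** The best argument for a change is that week 14 is a minimum. Any screening time, any delay between harvest and infusion, or counting visits from a later infusion widens the gap. Judging eligibility before leukapheresis is the natural order, and a sentence or two would settle both origins. The arithmetic and the natural order both stand.

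The rest is weaker. Two sentences might be cited to fix the origin at leukapheresis, and neither does so. In "The expansion rates of iNKT cells in enrolled patients before and after" cultivation, the before and after date the cell measurements, not enrolment. "Tegafur will be given twice per day for 2 weeks after apheresis" dates a drug, not the life-span judgement.

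The completion clause can also be read as an aim: the patient should be expected to finish, and in any case to live at least 12 weeks. On that reading someone not expected to reach the last visit is not clearly eligible. The open-ended follow-up favours this reading, because a literal guarantee would be impossible.

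The missing rule for early deaths is real, but the 2-week gap does not cause it. The SAP contains no safety analysis at all, so deaths before week 12 would lack a written counting rule whatever life span was required. That omission should be judged separately.

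**Conclusion.** No change follows. If life span is judged at or before leukapheresis, the criterion stops at least 2 weeks short of one of four scheduled safety visits. If life span and visits are both dated from first infusion, it stops short of none. The documents do not say which applies, so this is an unstated time origin and not a failed calculation.

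Each possible remedy gains little. Naming the two origins would be a useful clarification, but it fills in a detail that the people running the study must settle anyway. Removing the completion wording alters nothing that is done. Lengthening the criterion is an eligibility trade-off: it could exclude some of the sickest patients, and nothing in the documents shows that predictions of 12 and 14 weeks can be told apart. Reporting early deaths and withdrawals among all infused patients is what a sensible analyst would do without being told.

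The conclusion rests on the 4-week monitoring staying inside the criterion (week 6 on the first-infusion count, at most week 10 if the infusions span up to an assumed 4 weeks) and on both analysed outcomes being independent of the late visit. The number of patients predicted to live between 12 and 14 weeks cannot be computed, because the documents give no distribution of predicted life span.

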## **Method**

Patients underwent leukapheresis to collect circulating iNKT cells, which were isolated using a monoclonal antibody (6B11) against the invariant TCR- $\alpha$  chain expressed by iNKT cells and expanded in culture over 14 days. The expanded cells were harvested and divided into 3 doses. The expansion rates of iNKT cells in enrolled patients before and after

cultivation were analysed by flow cytometry analysis. Realtime-PCR was conducted to compare the mRNA level of Th1 and Th2 cytokines before and after iNKT cultivation.

### **Stuty design**

Patients were intravenously doped with different doses of autologous iNKT cells, 3 infusions per course. Dosages were escalated from  $3 \times 10^7$  cells/m^2 to at least  $9 \times 10^7$  cells/m^2. Tegafur will be given twice per day for 2 weeks after apheresis. Human IL-2 will be given during 5-14 days after iNKT cells infusion. Subjects were monitored for 4 weeks post-infusion to make sure the safety of this therapy. The laboratory safety tests and physical examination were carried out at 2nd week, 4th week, 8th week and 12th week after iNKT infusion. All subjects were followed every 3 months until the disease progressed.

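### Does it matter that the 4-week safety monitoring and the week 2 to 12 tests do not say which of the three infusions starts the clock?

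*Combined protocol and SAP*

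**What the plan says.** The background section describes a phase I dose escalation study of autologous iNKT cells. The method section says of the cell product: "The expanded cells were harvested and divided into 3 doses". The study design section matches this with "3 infusions per course".

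Three time references in the study design section then use infusion in the singular:

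- Safety monitoring: "Subjects were monitored for 4 weeks post-infusion to make sure the safety of this therapy".
- Laboratory tests and examinations at weeks 2 and 4 and at the "8th week and 12th week after iNKT infusion".
- Concomitant treatment: "Human IL-2 will be given during 5-14 days after iNKT cells infusion".

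Longer follow-up is also given without a stated start: "All subjects were followed every 3 months until the disease progressed".

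No section defines a day 0, names an index infusion or gives the interval between infusions. The statistical analysis plan covers only cell expansion and Th1/Th2 cytokine mRNA, compared before and after culture. It plans no safety analysis.

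**The concern.** In a dose escalation study, safety is the main thing the clinical follow-up has to deliver, and the 4-week window is given no other purpose. If the clock starts at the first infusion and the infusions are spread out, part or all of the 4 weeks passes before the course is complete. A test labelled week 2 might then follow one, two or three infusions. If staff used different clocks, the same adverse event could count inside the window for one patient and outside it for another, and dose levels would be described over unequal observation. The IL-2 period has the same undefined start.

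**Working it through.** **Inputs.** From the study design section: 3 infusions per course, monitoring for 4 weeks (4 × 7 = 28 days), tests at weeks 2, 4, 8 and 12 (days 14, 28, 56 and 84). The spacing is not stated. I assume equal gaps of d days and try d = 1, 3, 7 and 14. The third infusion then falls 2d days after the first. The plan has no figure of its own to reproduce.

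**Monitoring left after the third infusion.**

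- Clock on the first infusion: 28 − 2d days.
- Clock on the last infusion: 28 days, whatever d is.
- Four weeks after each infusion: 28 days after the third. The three windows join into one unbroken period from the first infusion to day 2d + 28, provided d is at most 28.

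**Tests under the first-infusion clock**, the only reading with a shortfall, in days relative to the third infusion:

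| Assumed d | Monitoring left, 28 − 2d | Week 2, 14 − 2d | Week 4, 28 − 2d | Week 8, 56 − 2d | Week 12, 84 − 2d |
|---|---|---|---|---|---|
| 1 | 26 | 12 | 26 | 54 | 82 |
| 3 | 22 | 8 | 22 | 50 | 78 |
| 7 | 14 | 0 | 14 | 42 | 70 |
| 14 | 0 | −14 | 0 | 28 | 56 |

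At d = 7 the week 2 test coincides with the third infusion, and at d = 14 the week 4 test does. The week 8 test still falls at least 28 days after the third infusion whenever 56 − 2d ≥ 28, that is d ≤ 14. The week 12 test does so whenever 84 − 2d ≥ 28, that is d ≤ 28.

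**IL-2.** Counted from the third infusion, its last day is 2d + 14 days after the first: 16, 20, 28 or 42. It passes day 28 only when d exceeds 7. This shows that the same word is undefined there too. It does not show that two statements conflict.

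**Effect on the analysis.** The quantities in the statistical analysis plan are measured on cells before and after culture, ahead of any infusion of the expanded product. No choice of clock can alter them. The documents also describe no escalation decision tied to the 4 weeks and no comparison of safety between dose levels.

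**What fixing the clock would do.** Counting the tests from the last infusion would secure 28 days of monitoring after it. It would also move the first scheduled test from day 14 to day 14 + 2d after the first infusion: day 16, 20, 28 or 42. No scheduled test would then fall between infusions.

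**The case for a change.** The best argument for a change is that the omission is plain, the study is phase I, and a few added words would settle it. Reading the window as running from the last infusion is plausible, but the text does not say so, and a reader of the safety results needs to know which clock was used. At a spacing of a week or more, the first-infusion reading would leave half or less of the stated 4 weeks after the full course.

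The ambiguity and the arithmetic both stand. The inference that the plan goes wrong does not. No stated rule is shown to give a wrong result, and two of the three readings already provide the observation wanted. Nothing in the documents supports a weekly or fortnightly spacing over a spacing of days. One harvest split into three doses, with no storage step described, does not settle the matter either way. The supposed harm to a comparison across doses has no planned comparison behind it. Nor does one choice of clock win outright: the last infusion gives longer observation at the end of the course, the first gives earlier testing during it.

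**Conclusion.** This is missing detail that those running and reporting the study can fill sensibly, so no change to the plan follows. The shortfall arises under one of three readings. It ranges from 2 of the 28 days at daily spacing (28 − 26) to all 28 at fortnightly spacing. In each case tried, later scheduled tests still reach at least 28 days beyond the third infusion. No planned calculation moves.

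This rests on two assumptions. First, the gaps are equal and no longer than those tried. With much longer gaps, the first-infusion reading would leave even the later tests close to the third infusion, or before it. Second, the dates of each infusion and adverse event are recorded, so that events can be tabulated by time since any infusion, whichever clock is adopted. The documents do not state this. A report of the study would naturally give the spacing and the clock used, including the start of IL-2. Which clock or schedule is right is not judged here.

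### Described safety observation starts at infusion, so the apheresis-to-infusion interval, when tegafur appears to be given, lies outside it, and no pre-treatment reference value is described

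*Combined protocol and SAP*

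**What the plan says.** The combined protocol and SAP is short, and three of its sections bear on this point.

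- **Study design (printed as Stuty design), treatment.** "Tegafur will be given twice per day for 2 weeks after apheresis". The cells follow: "Patients were intravenously doped with different doses of autologous iNKT cells, 3 infusions per course". Then "Human IL-2 will be given during 5-14 days after iNKT cells infusion". No patient or cohort is described as exempt from tegafur or IL-2.
- **Study design, safety observation.** "Subjects were monitored for 4 weeks post-infusion to make sure the safety of this therapy". The visit schedule comes next in the same section and opens so: "The laboratory safety tests and physical examination were carried out at 2nd week". Further visits are set for weeks 4, 8 and 12, all counted from iNKT infusion. No other safety schedule is given.
- **Method.** After leukapheresis the cells are isolated and "expanded in culture over 14 days". Only then: "The expanded cells were harvested and divided into 3 doses".
- **Objectives.** The exclusions include uncontrolled systemic disease and "positive HIV, syphilis or immune deficiency disease". These imply some screening, but no baseline safety test is listed.
- **Statistical Analysis Plan.** It covers cell expansion rates and cytokine mRNA before and after culture. It contains no safety analysis.

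**The concern.** Treatment under the protocol begins before the first infusion. Patients undergo apheresis and, it appears, take tegafur while their cells are in culture. Every safety observation that the document describes is timed from infusion. Two things follow if the schedule is applied as written.

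First, adverse events between apheresis and first infusion belong to the safety of the treatment course but have no place in a summary that starts at infusion. The toxicity of the course could be understated.

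Second, the earliest described laboratory test is at week 2 after infusion, with no described earlier value to read it against. In patients with advanced hepatocellular carcinoma an abnormal week-2 value is ambiguous. It may have been there at entry, arisen during tegafur, or arisen since infusion. In a phase I dose-escalation trial these distinctions matter for what is reported at each cell-dose level.

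**Working it through.** The plan states no figure to reproduce. The check is a day count with apheresis as day 0.

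**Inputs**
- Tegafur: 14 days, after apheresis (Study design). Start day *s* is not given.
- Culture: 14 days between apheresis and harvest (Method).
- First infusion: day 14 + *d*, where *d* ≥ 0 is any delay after harvest. The value of *d* is not given.
- Safety monitoring: 28 days from infusion (Study design).
- Tests and examinations: 14, 28, 56 and 84 days after infusion (weeks 2, 4, 8 and 12; Study design).

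Infusion is counted from the first of the three, the reading that starts observation earliest.

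**Step 1: interval before any described safety observation.** This is 14 + *d* days, so at least 14 days, whenever tegafur starts.

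**Step 2: tegafur days before the window.** Tegafur runs from day *s* to day *s* + 14, and the window opens on day 14 + *d*. The overlap is (*s* + 14) − (14 + *d*) = *s* − *d* when that is positive, and otherwise 0. Tegafur days before the window = 14 − max(0, *s* − *d*).

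| Assumed *s* | Assumed *d* | Tegafur days before the window |
|---|---|---|
| 0 | 0 | 14 − 0 = 14 of 14 |
| 3 | 0 | 14 − 3 = 11 of 14 |
| 7 | 0 | 14 − 7 = 7 of 14 |
| 7 | 7 | 14 − 0 = 14 of 14 |

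The count is 14 of 14 whenever tegafur starts no later after apheresis than infusion follows harvest (*s* ≤ *d*). It falls below that only with a delayed tegafur start and prompt infusion.

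**Step 3: time to the first described test.** With *s* = 0 and *d* = 0, monitoring covers days 14 to 42, and the tests fall on days 14 + 14 = 28, 14 + 28 = 42, 14 + 56 = 70 and 14 + 84 = 98. The first test is then 28 days after tegafur starts and 14 days after it ends. If the infusion that anchors the visits is 0 to 14 days after harvest (assumed), the first test is 28 to 42 days after tegafur starts.

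**Step 4: described reference values.** Safety tests described before tegafur: 0. Described between the end of tegafur and the first infusion: 0.

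**Step 5: what can be said of an abnormality first seen at week 2.**

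| Values available | What can be told apart |
|---|---|
| None (as described) | Nothing: all three origins remain open |
| Pre-apheresis only | Present at entry, or new since apheresis |
| Pre-apheresis and last pre-infusion | Present at entry, new between apheresis and infusion, or new since infusion |

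Both values are needed for the three-way distinction.

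**The case against.** The strongest reply is that this is a brief summary with no adverse-event section at all, so silence about a baseline or about the tegafur period does not mean that nothing was recorded. That stands. A reader might infer that patients went unobserved during tegafur, or that no baseline blood was taken. The text supports neither: it shows only that no such observation is described. The exclusion of uncontrolled systemic disease, HIV and syphilis suggests that some pre-treatment assessment took place.

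The timing is also inferred, and that stands too. A delayed tegafur start could place part of the period after infusion. So could a second course, if courses were repeated, which the document does not say. What does not depend on the tegafur start day is the interval of at least 14 days between apheresis and first infusion with no described safety observation. Tegafur effects that persist or emerge after infusion would still be picked up.

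A reader might go further and say that the trial wrongly claims safety for the cells alone. No such conclusion appears in the document. The study-design section lists tegafur and IL-2 openly, its phrase about the safety of the therapy may already mean the whole regimen, and the absence of a cells-only cohort is a phase I design choice. The label proposed below is a precaution and corrects no existing sentence.

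Nor does the text allow a firm share of the whole treatment period that goes unobserved, or a count of tests falling before IL-2. Both depend on infusion spacing and on which infusion anchors the schedule, and neither is stated. That anchor, and whether the IL-2 interval is a window or a duration, need separate clarification.

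Finally, much of the text is in the past tense, so part of the remedy may come too late.

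**Conclusion.** The concern holds in a limited form and should be addressed. As described, safety observation opens at infusion, leaving at least 14 days from apheresis outside it. About 14 of 14 tegafur days fall in that gap if tegafur starts at or soon after apheresis. No safety value from before tegafur or before the first infusion is described, so abnormalities first seen at week 2 could not be placed in time.

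This rests on two assumptions: that the culture takes its full 14 days, and that tegafur begins close to apheresis. A later tegafur start lowers the tegafur count but does not close the gap. Confidence is medium because the document is brief and the relevant records may exist without being mentioned.

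**What to change.** Treatment stays as it is. Three changes to the text:

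(a) **Study design.** Start adverse-event recording at apheresis instead of at infusion.

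(b) **Study design.** Define two reference values for the safety tests: the pre-apheresis value, and the last value before the first infusion. Take them from tests already done where they exist, and otherwise from one routine blood test.

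(c) **Statistical Analysis Plan.** Add a descriptive table. Suggested wording: *Adverse events and laboratory abnormalities will be tabulated by cell-dose level, separately for onset from apheresis to first infusion and onset after first infusion, with laboratory change shown against both reference values. The table describes the safety of the regimen of tegafur, iNKT cells and IL-2.* The regimen label follows from every patient being described as receiving all three.

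**Cost.** About 14 more days of event recording per patient, possibly one routine test per patient, and one table. Its cells may be sparse, since no sample size is stated, and onset periods order events in time without proving cause.

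If conduct is already complete, only (c) on events already recorded and (b) from existing values can be applied. The report should then say what was and was not recorded before infusion.
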